7.5.3 Accountability of Investigational Product

The investigator must keep an accurate accounting of the number of IP units delivered to the site, dispensed to subjects, returned to the investigator by the subject, and returned to the sponsor or other disposition during and at the completion of the study.

7.5.3.1 Receipt of Investigational Product

Upon receipt of the IP, the investigator or delegate must conduct an inventory. During the study, the investigator or designated study staff must provide the IP to the subjects.

Throughout the study, the investigator or delegate must maintain records of IP dispensation and collection for each subject. This record must be made available to the study monitor for the purposes of verifying the accounting of IP supplies. Any discrepancies and/or deficiencies between the observed disposition and the written account must be recorded along with an explanation. All IP sent to the investigator must be accounted for by study sponsor personnel, and in no case be used in an unauthorized situation.

7.5.3.2 Return of Investigational Product

When the site is closed, the study is completed or is terminated by the sponsor, all unused IP will be returned to the sponsor (or the sponsor's designee). The investigator is responsible for proper disposition of all used IP at the conclusion of the study after IP reconciliation, according to the instructions provided in the MOP. All IP reconciliation procedures must be completed before the study is concluded. The responsible person at the investigator's institution must account for all used and unused IP. The IP storage manager or designee will complete a study drug returns form or equivalent that will be signed by the investigator or designee prior to returning the unused IP to the sponsor's designee.

7.6 Subject Assignment, Randomization, and Masking

7.6.1 Subject Assignment

Subject assignment is not applicable in this single-arm design, with one IP, as all subjects who meet the inclusion/exclusion criteria will receive the same IP.

7.6.2 Masking and Unmasking

All members associated with the study (at the site and the study sponsor) are unmasked to the assigned IP.

7.7 Investigational Product Compliance

Compliance with IP usage will be assessed at Visit 3/Remote Compliance Check and Visit 4/Exit. [REDACTED]

7.8 Concomitant Therapy

Pharmacologic and nonpharmacologic therapies and surgeries/procedures will be queried during Visit 1/Screening.

7.8.1 Prohibited Concomitant Therapy

The table below outlines all prohibited prior and concomitant therapies. Subjects must discontinue the use of any of the therapies or interventions listed in [Table 7-2](#) for the specified period prior to the specified visit and these therapies or interventions must not be used during the course of the study. Use of any of these therapies or interventions during the course of the study must be documented as a protocol deviation.

Table 7-2 Prohibited Concomitant Therapies

Intervention/Therapy	Washout Required	Precaution(s) and Action(s) to be Taken	Rationale
Topical ocular medications preserved with benzalkonium chloride. Examples include: Travatan, Xalatan, Lumigan, etc.	A month before the Screening visit until subject is exited from the study.	Discontinue subject from study if taken concomitantly during IP administration.	May confound primary efficacy variable.
Any artificial tear products. Examples of prohibited ocular lubricants include: Blink, Refresh, Biotrue, other Systane products, iVizia, Visine, Soothe, etc. See exclusion criteria number 14 (Section 6.3)	From the beginning of the Baseline visit until subject is exited from the study.	Discontinue patient from study if any ocular lubricant is taken concomitantly with IP for more than 2 consecutive days.	May confound primary efficacy variable.

8 DISCONTINUATION OF INVESTIGATIONAL PRODUCT AND SUBJECT WITHDRAWAL FROM STUDY

8.1 Discontinuation of Investigational Product

Discontinuation of IP for a Subject occurs when IP is stopped earlier than the protocol planned duration.

8.1.1 Criteria for Permanent Discontinuation of Investigational Product

A subject may be discontinued from IP at the discretion of the investigator or the medical monitor. Other reasons that a subject may be discontinued from IP may include, but are not limited to:

- *Adverse event(s) (AEs including, in the opinion of the investigator, clinically relevant laboratory abnormalities, and intercurrent diseases reported by the subject or observed by the investigator)
- ^Pregnancy

*AE may result in discontinuation of IP; however, it is up to discretion of the investigator if subject should continue safety assessments in the study.

^Pregnancies occurring in subjects enrolled in the study must be reported and followed to outcome. No further study treatments will be administered to pregnant subjects; however, the subject will be encouraged to complete all safety assessments in the study.

Subjects that discontinue IP and continue in the study should continue safety assessments.

8.1.2 Temporary Discontinuation or Interruption of Investigational Product

Subjects who have to interrupt treatment for any reason should be discontinued from participation in the study at the investigator's discretion. Subjects who miss a dose(s) of IP should resume administration at their earliest convenience [REDACTED]

[REDACTED] Subjects should aim to use the minimum required dosage.

Every effort must be made to keep the subject in the study and to continue with the study assessments as specified in to [Table 2-2](#) and [Section 2.3](#) until the final visit.

8.1.3 Rechallenge

Subjects that experience an AE and have discontinued IP will not be rechallenged. However, this does not apply to suspected or expected AEs (e.g., eye redness, ocular discomfort, or temporary blurring of vision) that are reported without subject discontinuation/will not be considered rechallenged.

8.2 Subject Withdrawal from the Study

A subject may exit the study by their own volition. Any subject may decide to voluntarily withdraw from the study at any time without prejudice. The sponsor may retain and continue to use any data collected before such a withdrawal of consent.

If possible, an early exit visit should be conducted, in accordance with to [Table 2-2](#) and Section [2.3](#). IP will be discontinued upon subject exit.

The investigator must document the reason for study or IP discontinuation in the subject's case history source documents.

To ensure the safety of all subjects who discontinue early, investigators must assess each subject and, if necessary, advise them of any therapies and/or medical procedures that may be needed to maintain their health.

A subject may be withdrawn from the study at the discretion of the investigator or the medical monitor. Other reasons that a subject may be withdrawn from the study may include, but are not limited to:

- Adverse event(s) (AEs including, in the opinion of the investigator, clinically relevant laboratory abnormalities, and intercurrent diseases reported by the subject or observed by the investigator)
- Death
- Lack of efficacy
- Lost to follow-up
- Pregnancy
- Protocol violation (specify)
- Study terminated by sponsor
- Technical problems
- Withdrawal by subject (specify)
- Other (specify)

8.3 Lost to Follow-up

A subject will be considered lost to follow-up if he/she repeatedly fails to return for scheduled visits and is unable to be contacted by the study site.

The following actions must be taken if a subject fails to return to the clinic for a required study visit:

- The site must attempt to contact the subject and reschedule the missed visit as soon as possible, counsel the subject on the importance of maintaining the assigned visit schedule, and ascertain whether the subject wishes to and/or should continue in the study.
- Before a subject is deemed lost to follow-up, the investigator or designee must make every effort to regain contact with the subject (where possible, 3 telephone calls, and if necessary, a certified letter to the subject's last known mailing address or local equivalent methods). These contact attempts should be documented in the subject's medical record.
- Should the subject continue to be unreachable, he/she will be considered to have withdrawn from the study.

8.4 Follow-up of Subjects After Study Participation has Ended

Following this study, the subject will return to their eye care professional for their routine eye care.

8.5 Study Stopping Rules

N/A

9 STUDY ASSESSMENTS AND PROCEDURES

Detailed descriptions of assessments and procedures are provided in the MOP. The investigator is responsible for ensuring that responsibilities for all procedures and assessments are delegated to appropriately qualified site personnel.

9.1 Screening/Baseline Assessments and Procedures

The investigator or delegate must explain the purpose and nature of the study, and have the subject read, sign, and date the IRB/IEC-approved ICF. The subject must sign the ICF BEFORE any study-specific procedures or assessments can be performed, including study-specific screening procedures. Additionally, have the individual obtaining consent from the subject and a witness, if applicable, sign and date the ICF.

The investigator or delegate must provide a copy of the signed document to the subject and place the original signed document in the subject's chart, or provide documentation as required by local regulations.

9.1.1 Connect to Electronic Patient Reported Outcomes

At Screening, subjects must connect to ePRO with their mobile device after signing the ICF and prior performing any other assessments. If subject is unable to connect, the Screening visit can be rescheduled within a maximum of 7 days/1 week to allow the subject to meet inclusion criteria number 9. All remaining eligibility criteria will be verified after completing inclusion criteria number 9.

9.1.2 Demographics

Obtain relevant demographic information including age, race, ethnicity, sex, etc.

9.1.3 Medical/Ophthalmic History

Significant medical and ophthalmic history will be collected at Screening, including:

- Current medical/ophthalmic conditions
- Medical/ophthalmic conditions that began within the last 12 months and which may have resolved before Screening
- Resolved medical/ophthalmic conditions that are deemed relevant by the investigator
- Relevant surgeries/procedures

Throughout the subject's participation, obtain information on any changes in medical health. Medical history will be collected in the eCRF as outlined in the MOP.

9.1.4 Prior and Concomitant Medication Assessments

Any medication (including vaccines, OTC or prescription medicines, vitamins, and/or herbal supplements) will be queried and recorded on the appropriate case report form and updated at each visit. Prior medications taken up to 30 days prior to the Screening must also be recorded.

Concomitant medications will be collected in the eCRF as outlined in the MOP.

9.1.5 Urine Pregnancy Test

Women who are pregnant or breastfeeding are excluded from participation in the study. A urine pregnancy test will be performed at Visit 1/Screening, Visit 4/Exit, Early Exit, and Unscheduled Visits (as necessary) in all females of childbearing potential.

9.2 Efficacy Assessments and Procedures

9.2.1 IDEEL-SB Questionnaire

IDEEL-SB Questionnaire score will be completed by the subject at Visit 1/Screening and Visit 4/Exit Day 30 ± 5/Early Exit.

9.3 Safety Assessments and Procedures

9.3.1 Adverse Event Collection

Assess and record any adverse events that are observed or reported since the previous visit, including those associated with changes in concomitant medication dosing.

9.3.2 Device Deficiency Collection

Assess and record any device deficiencies that are observed or reported since the previous visit.

9.3.3 Slit Lamp Biomicroscopy

SLE of the cornea, conjunctiva, eyelids, and ocular surface must be performed in both eyes.

9.3.4 Best Corrected Visual Acuity

LogMAR visual acuity using the ETDRS and/or SOC chart for both eyes must be performed.

9.3.5 Unscheduled Visits

If a subject visit occurs between any regularly scheduled visit and the visit is conducted by study personnel, this visit must be documented as an Unscheduled Visit. If the subject seeks medical attention outside the clinic (for example, at an emergency room) or at the clinic but is seen by non-study personnel, the investigator is to capture adverse event-related information on the adverse event form upon becoming aware.

If a subject experiences any symptoms of eye infections, including but not limited to eye pain, eye redness, eye irritation, they need to schedule an Unscheduled Visit and seek medical advice or treatment.

During an Unscheduled Visit (for an adverse event), the investigator must conduct the following procedures:

- Collect adverse event and device deficiencies information
- Record changes in medical condition or concomitant medication
- Perform BCVA
- Perform slit lamp biomicroscopy exam

The investigator may perform additional procedures for proper diagnosis and treatment of the subject. The investigator must document this information in the subjects' case history source documents.

If during an Unscheduled Visit the subject is discontinuing the IP or discontinuing from the study, the investigator must conduct Exit procedures according to [Table 2-2](#), as possible.

Spare IP is not dispensed to the subject in this study. If IP is lost, damaged, or needs to be replaced due to an AE/device deficiency, the subject will be instructed to return for an unplanned dispense visit. Refer to the MOP for more details.

9.4 Adverse Events and Serious Adverse Events

9.4.1 Definitions of AE and SAE

The following definitions of terms apply to this section:

- Adverse event (AE): Any untoward medical occurrence in a patient or clinical investigation subject administered a pharmaceutical product and which does not necessarily have a causal relationship with this treatment. An AE can therefore be any unfavorable and unintended sign (including an abnormal laboratory finding), symptom, or disease temporally associated with the use of a medicinal (investigational) product, whether or not related to the medicinal (investigational) product.
- Adverse drug reaction (ADR): All noxious and unintended responses to a medicinal product related to any dose should be considered ADRs. Responses to a medicinal product means that a causal relationship between a medicinal product and an adverse event is at least a reasonable possibility, i.e., the relationship cannot be ruled out.
- Adverse Event of Special Interest (AESI): Adverse event (serious or nonserious) of scientific and medical concern specific to the sponsor's product or program, for which ongoing monitoring and rapid communication by the investigator to the sponsor can be appropriate. Such an event might warrant further investigation in order to characterize and understand it. Depending on the nature of the event, rapid communication by the trial sponsor to other parties (e.g., regulators) might also be warranted.
- Life-threatening AE or life-threatening ADR: an AE or ADR is considered "life-threatening" if, in the view of either the investigator or sponsor, its occurrence places the subject at immediate risk of death. It does not include an AE or ADR that, had it occurred in a more severe form, might have caused death.
- Serious adverse event (SAE) or serious adverse reaction (SAR): an AE or AR is considered "serious" if, in the view of either the investigator or sponsor, it results in any of the following outcomes:
 - Death, a life-threatening or sight-threatening AE,

- a subject hospitalization or prolongation of existing hospitalization, Note: Planned hospitalization for a preexisting condition, without serious deterioration in health, is not considered a serious adverse event. Therefore, neither the condition, hospitalization, prolonged hospitalization, nor surgery are reported as a serious adverse event when the hospitalization or prolonged hospitalization was for an elective surgical procedure or for a preexisting condition. In general, hospitalization signifies that the individual remained at the hospital or emergency ward for observation and/or treatment (usually involving an overnight stay) that would not have been appropriate in the physician's office or an outpatient setting. Complications that occur during hospitalization are adverse events. If a complication prolongs hospitalization or fulfills any other serious criteria, the event is serious. When in doubt as to whether “hospitalization” occurred, the event should be considered serious.
- a persistent or significant incapacity or substantial disruption of the ability to conduct normal life functions (disability), or
- a congenital anomaly/birth defect
- Important medical event or reaction that may not result in death, be life-threatening, or require hospitalization may be considered serious when, based upon appropriate medical judgment, they may jeopardize the subject and may require medical or surgical intervention to prevent one of the outcomes listed in this definition. Examples of such medical events include allergic bronchospasm requiring intensive treatment in an emergency room or at home, blood dyscrasias, or convulsions that do not result in subject hospitalization, or the development of drug dependency or drug abuse.

Note: Medical and scientific judgment should be exercised in deciding whether other situations should be considered as serious such as important medical events that may not be immediately life-threatening or result in death or hospitalization but may jeopardize the subject or may require intervention to prevent one of the other outcomes listed in the definition above. These should also be considered serious.

Examples of such events are intensive treatment in an emergency room or at home for allergic bronchospasm, blood dyscrasias or convulsions that do not result in hospitalization, or development of drug dependency or drug abuse.

- Suspected unexpected SAR (SUSAR): Adverse drug reaction that is both unexpected and meets the definition of a serious adverse event.
- Unexpected AE or unexpected ADR: an AE or ADR is considered “unexpected” if it is not listed in the IB or is not listed at the specificity or severity that has been observed; or, if an IB is not required or available, is not consistent with the risk information described in the general investigational plan or elsewhere in the current application, as amended.

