Investigational Product	A preventative (vaccine), a therapeutic (drug or biologic), device, diagnostic, or palliative used as a test or comparator product in a clinical study, including a product with a marketing authorization when used or assembled (formulated or packaged) in a way different from the authorized form, or when used for an

Term	Definition
	unauthorized indication, or when used to gain further information about the authorized form.
Nonserious Adverse Event	Adverse event that does not meet the criteria for a serious adverse event.
Point of Enrollment	The time at which, following recruitment and before any clinical investigation-related procedures are undertaken, a subject signs and dates the informed consent form.
Screen Failure	A subject who did not meet one or more criteria that were required for participation in the study.
Screening	A process of active evaluation of potential subjects for enrollment in a study. After a patient is recruited, screening occurs during the enrollment period, after informed consent has been obtained, to see if they meet the inclusion and exclusion criteria. If they meet the criteria, the subject is eligible to enroll in the study.
Serious Adverse Event (SAE)	
Any untoward medical occurrence that at any dose:
 
 results in death, is life-threatening, 
Note: Life-threatening means that the individual was at immediate risk of death from the event as it occurred, i.e., it does not include an event which hypothetically might have caused death had it occurred in a more severe form.
 
 requires inpatient hospitalization or prolongation of existing hospitalization, 
Note: Planned hospitalization for a preexisting condition, without serious deterioration in health, is not considered a serious adverse event.
 
 results in persistent or significant disability/incapacity, is a congenital anomaly/birth defect, or is a medically important event or reaction. 
Note: Medical and scientific judgment should be exercised in deciding whether other situations should be considered as serious such as important medical events that may not be immediately life-threatening or result in death or hospitalization but may jeopardize the patient or may require intervention to prevent one of the other outcomes listed in the definition above. These should also be considered serious.

Term	Definition

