9.4.6 Reporting of SAEs

An investigator must immediately (i.e., within 24 hrs) report any SAE or SAR to the sponsor or sponsor representative, whether or not considered trial intervention-related, including those listed in the protocol or IB. The investigator must use the SAE report form (eCRF or email as a back-up) and include an assessment of whether there is a reasonable possibility that the trial intervention caused the event. The investigator must report any SAE or SAR that occurs or is observed during the trial. In case of incomplete information, the investigator must provide follow-up information as soon as possible, again using the SAE report form. The details for SAE/SAR report submission are listed below.

Report SAEs/SARs within 24 hrs via electronic data capture (EDC) system or, in the case of the EDC system not being available, the provided SAE source document will be completed and sent via the instructions noted on the form to the sponsor representative within the expected reporting time frame.

SAE/SAR reports will be evaluated by the medical monitor. Regulatory authorities, IRB/IEC, and investigators at each of the trial sites will be informed as required.

An assessment of seriousness will also be performed for all adverse events by a sponsor physician utilizing the same criteria. If an adverse event reported for an investigator's subject is upgraded to a serious adverse event by a sponsor physician, the investigator will receive a notification from the sponsor.

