9.4.10 Disease-related Events or Outcomes Not Qualifying as AEs or SAEs

Any medical condition present prior to informed consent which remains unchanged or improved should not be recorded as an AE at subsequent visits. However, an AE should be recorded if the frequency, intensity, or the character of a preexisting condition worsens during the trial period beyond what would be expected from the natural progression of that condition.

Surgery should not be reported as an adverse event nor as an outcome of an adverse event if the purpose of the surgery was diagnostic and the outcome was uneventful.

If there is a question as to whether a medical development should be reported as an adverse event, it is recommended the investigator contact the sponsor for guidance.

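### One sentence in Protocol 9.4.1 omits two qualifiers and can be read to exempt unplanned admissions for a worsened pre-existing condition from SAE reporting, which Table 1-1 would class as serious

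*Protocol*

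**What the plan says.** Table 1-1 of the Protocol makes an event serious if it "requires inpatient hospitalization or prolongation of existing hospitalization". It allows one exemption: "Planned hospitalization for a preexisting condition, without serious deterioration in health, is not considered a serious adverse event".

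Section 9.4.1, whose definitions are stated to govern that section, also counts hospitalization as a serious outcome. Its note opens with the same exemption, word for word. It then adds a reporting instruction that Table 1-1 does not have: "Therefore, neither the condition, hospitalization, prolonged hospitalization, nor surgery are reported as a serious adverse event". The second half of that instruction sets out the circumstances in which it applies, namely "when the hospitalization or prolonged hospitalization was for an elective surgical procedure or for a preexisting condition".

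Three other provisions bear on the point:
- Complications during a stay, in the same note: "If a complication prolongs hospitalization or fulfills any other serious criteria, the event is serious".
- Doubt, also in the same note. If it is unclear whether hospitalization "occurred, the event should be considered serious".
- Worsening of an existing condition, in 9.4.10: "an AE should be recorded if the frequency, intensity, or the character of a preexisting condition worsens during the trial period". The sentence goes on to require worsening beyond natural progression.

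Under 9.4.6, SAEs go to the sponsor within 24 hours and are evaluated by the medical monitor. The same section adds: "An assessment of seriousness will also be performed for all adverse events by a sponsor physician utilizing the same criteria".

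**The concern.** The reporting instruction is wider than the exemption it is said to follow from. An investigator who applies it as written could leave an emergency admission for a worsened condition off the SAE form, while Table 1-1 offers no exemption for it.

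The case can arise. Exclusion criterion 4 removes unstable diabetes and poorly controlled hypertension, so subjects whose disease is controlled are not barred by it, and there is no upper age limit.

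Seriousness feeds two outputs. One is the 24-hour report. The trial has no committee (12.2) and no stopping rules (8.5), and 9.4.7 states that SAEs need not be reported to the health authority, so this is the main rapid route by which such an event is seen. The other is the pair of serious TEAE tables, ocular and nonocular, in SAP 5.3.1. SUSAR status also depends on the SAE definition.

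**Working it through.** No arithmetic applies. The check is to compare the scope of the two sentences and then run test cases through each rule.

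**Scope of the exemption**
- Table 1-1 and the first sentence of the 9.4.1 note: the admission must be planned, for a pre-existing condition, and without serious deterioration. All three must hold.
- The *Therefore* sentence: either an elective surgical procedure or a pre-existing condition is enough. Neither qualifier is repeated. It also covers prolonged stays and removes the condition itself from SAE reporting, not only the admission.

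**Test cases** (each is an inpatient stay; any worsening is taken to exceed natural progression and to be a serious deterioration)

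| Case | Table 1-1 | *Therefore* sentence, bound by the sentence before it | *Therefore* sentence, literal |
|---|---|---|---|
| Planned admission, pre-existing condition, no deterioration | Exempt | Exempt | Exempt |
| Unplanned admission for a worsened pre-existing condition | Serious | Serious | Not reported as SAE |
| Elective operation for a condition that first arose on study | Serious | Serious | Not reported as SAE |

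The readings agree on the first row and split on the other two. The second row matters most, because an unplanned admission for worsening is what the two qualifiers keep outside the exemption.

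**Do the other provisions close the gap?**
1. The complication rule concerns what happens during a stay, not the reason for admission. It may rescue some prolonged stays, but there it pulls against the literal *Therefore* sentence, which exempts prolongation for a pre-existing condition.
2. The doubt rule resolves whether a hospitalization took place. In the second row nobody doubts that it did.
3. The sponsor physician's review is a second look at every AE, but it applies the same criteria and so inherits the same sentence.
4. The separate criteria (life- or sight-threatening, disability, important medical event) would catch some admissions. An ordinary unplanned admission may meet only the hospitalization criterion.
5. Section 9.4.10 makes the worsening an AE and sets no seriousness rule. It leaves the second row open.

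None of the five settles the second row in general.

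**The case against.** The best defence is grammatical. The qualifiers have not left 9.4.1; they stand in the sentence immediately before, and *Therefore* presents what follows as a consequence of it. A site working from 9.4.1 meets the qualified sentence first. On that reading an unplanned admission for worsening remains an SAE and Table 1-1 is respected.

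This stands far enough to rule out a stronger reading. A reader might infer that 9.4.1 settles the matter and that such admissions will not be reported as serious. The text does not support that; it supports two readings. But the defence does not remove the ambiguity, because the second sentence goes beyond its premise. Elective surgery enters as an alternative not tied to a pre-existing condition. Prolonged stays enter too, and a prolongation is seldom planned, so that qualifier does not carry over naturally.

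A reader might also infer that 9.4.1 contradicts 9.4.10. It does not. One governs recording as an AE and the other governs reporting as an SAE, and a site can follow both. Section 9.4.10 helps only indirectly: it makes the worsening an AE, which Table 1-1 then makes serious if the subject is admitted.

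The consequence is also limited. The event is not lost from the safety data. If it meets 9.4.10 it is recorded as an AE and, if treatment-emergent, appears in the SAP's tables and listings of all such events. Seriousness may be judged by either the investigator or the sponsor, and the sponsor physician can upgrade an event. The safety analyses are descriptive, with no hypotheses.

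**Conclusion.** The point holds as an inconsistency of wording. The *Therefore* sentence omits both qualifiers and can be read to exempt an unplanned admission for a worsened pre-existing condition, which Table 1-1 would class as serious. The possible harm is misclassification: an event recorded as a nonserious AE, absent from the 24-hour report and from the serious TEAE tables.

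Its size cannot be stated as a number. A reader might want to say what share of the SAE table would be lost among about 185 subjects, but neither document gives an expected SAE rate, and any count would be a guess. The numbers are likely to be small in a study of about 37 days per subject. The primary efficacy analysis is unaffected, since the t-test on change in IDEEL-SB makes no use of seriousness.

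The conclusion assumes that some sites, of about 20, would follow the reporting sentence as written, and that the event meets no other seriousness criterion. It should be corrected because misclassification of this kind cannot be seen from the SAE tables afterwards and the correction is nearly free.

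**What to change.** Reconcile 9.4.1 with Table 1-1. Either repeat the two existing qualifiers in the *Therefore* sentence, so that its surgery and prolonged-stay wording falls under the same limits, or delete the sentence. Only a planned hospitalization for a pre-existing condition without serious deterioration in health would then be exempt, as Table 1-1 already says. No new term or cut-off is needed, and 9.4.10, the complication rule and the doubt rule can stay as they are. Tell sites of the clarification. If any hospitalizations have already been recorded, check their classification against the clarified wording before database lock.

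The cost is one sentence of protocol wording and a note to sites. The SAP refers to the protocol for its AE definition, so its tables need no change. The only downside is that a few more events may be reported as serious.
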